Since the clinical trial is structured to occur in cohorts, the longitudinal multilevel modeling (growth modeling) analysis will be run after each cohort is completed. Despite early cohorts being underpowered, we find significant value in understanding if the data are trending in the expected directions, and/or if there are any issues that need to be addressed. The methodologist running the analysis will remain unblinded throughout the analysis process. There are no temporary suspension or safety findings that would prompt temporary suspension of the treatment. The frequency of monitoring the end points is daily as older adult participants are on a rolling recruitment and finishing their treatment at different points in time. There is no effect of the interim analysis on the final analysis as it is the same analysis. Type I error results when running many different types of tests, however we are running the main analysis with an underpowered sample so that we are learning and understanding as we go. The final analysis will be the same code just with all the participants across all 4 cohorts.

---

7. 9.4.7 SUB-GROUP ANALYSES

Sub-group analyses on the primary endpoints will be assessed in two ways: (a) multi-level modeling by treatment severity group (same primary analysis, conducted independently for low, medium, and high risk patients), and (b) cluster analysis to explore any potential differential treatment effects across predefined patient subgroups (e.g., age, sex, race, etc.). Interaction terms between any subgroup variables (i.e. age, sex, baseline severity) and treatment condition will be included to assess whether the trajectory of outcomes over time varied by subgroup. This approach will enable the examination of both between- and within-patient variability while accounting for repeated measures and clustering.

Since the secondary endpoints are serving as a fidelity check (i.e. trained helpers increased skills, retained skills, etc.) and were are only planning for approximately 60 trained helpers, which would be under powered, any differences in sub-groups, we imagine will be challenging to detect. Despite this,

RMANOVA assesses mean differences across multiple time points, accounting for the within-subject correlation inherent in repeated measurements. Sub-group analysis will include testing interaction effects between time and categorical subgroup variables (e.g., age, sex, race) to determine if outcome trajectories differ across these groups.

---

8. 9.4.8 TABULATION OF INDIVIDUAL PARTICIPANT DATA

While individual participant data will be tracked by measure and time point, results will be presented in group form.

---

9. 9.4.9 EXPLORATORY ANALYSES

In addition to the main clinical trial analysis, and sub-group analyses this team will run a series of additional analyses to learn the most from this trial. These include a series of moderation analyses, both cross-sectionally and longitudinally, as there is literature to support rurality as a moderator, as well as the therapeutic alliance. We also plan to run an analysis on the long-term effects of the treatment. We will analyze qualitative data using Consensual Qualitative Research methodology, as well as Content Analysis to look both across participants, and deeply at each treatment dosage of a random sample of participants. Finally, we will be evaluating the treatment dosages by applying a quantitative coding protocol and running additional multilevel modeling, and triangulation between the measurement data described above and these coded audio files of treatment dosages.

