## 2. 6.3 MEASURES TO MINIMIZE BIAS: RANDOMIZATION AND BLINDING

We will use weighted stratified random assignment. After participants are baselined, we will score their data and assign them a risk tier (low, medium, high). Subsequently, we will randomize them to one of 3 conditions: BE condition, BE + ASIST condition, or control. Since the trial is being conducted in cohorts (waves), and to ensure the least amount of time between being baselined and starting the treatment, participants will be randomized one by one after they are baselined. The weighted component enables there to be equal representation of both risk tier and number of participants across all 3 treatment conditions within the confines of the ongoing nature of the trial.

At the time of baseline, participants are assigned 2 codes: one that is fully numeric, and another that is alphanumeric. The PI and graduate student(s) will have access to the unblinded data (i.e. both the older adults' names, codes, and baseline data) as the PI is supervising the process and a few graduate students will be helping with scoring, and the weighted stratified random assignment. The methodologist will only have access to the participants' codes and raw data. They will remain blind to ensure the most objective analysis of the data.

If a participant remains at elevated risk for suicide at the conclusion of the treatment, we will unblind them and report to their assigned case manager.

We will also use separate documents with participant codes only to track the following: treatment condition, rebaselines, any survey/measurement issues, risk tiers, etc. to ensure an additional level of rigor in protecting against any bias. Further, in all tracking files that the PI's research lab utilizes, only participant IDs will be utilized (i.e. tracking which participants are up for the next measurement occasion, etc.).

The only potential inadvertent unblinding that we could foresee would be with respect to the use of the Friendlybuzz system. The treatment providers do need to know the first names of the older adult participants, therefore ONLY their first names will be available. The data team, however, is completely distinct from the treatment team, and will not have access to the Friendlybuzz system.

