### 4. 10.1.4 FUTURE USE OF STORED SPECIMENS AND DATA

After the study is completed, the de-identified, archived data will be stored, and made available for use by other researchers including those outside of the study if deemed appropriate. Data will not be transmitted to any other entity unless the PI moves universities.

---

 5. 10.1.5 KEY ROLES AND STUDY GOVERNANCE

Principal Investigator	Medical Monitor or Independent Safety Monitor
[name], Ph.D., Associate [name]. [name]., Professor
University of Florida	University of Tennessee
[name]	[name]
[contact]	[contact]
[contact]	[contact]

---

 6. 10.1.6 SAFETY OVERSIGHT

Safety oversight will be accomplished through a quality assessment by an outside external evaluator, [name] [name], a full professor with program evaluation expertise, millions of dollars in external funding, and leadership roles in this content area. She is independent from the study, free of conflicts of interest, and will conduct evaluations prior to the start of the trial, monitoring checks during it, and then a formalized evaluation after the trial is complete with all levels of participation (i.e. research team members, leadership, trained helpers providing the treatment, participants, etc.).

---

 7. 10.1.7 CLINICAL MONITORING

Clinical coordinators will lead weekly accountability groups with trained helpers. These individuals will monitor the administration of the treatment, timing, call dose duration, and provided regular and routine feedback to the trained helpers providing the treatment.

---

 8. 10.1.8 QUALITY ASSURANCE AND QUALITY CONTROL

The PI and methodologist (Drs. [name] and [name]) will perform internal quality management of survey data (baseline and 5 measurement occasions) as well as the audio file and transcript data. Quality control (QC) procedures will be implemented as follows:

**Informed consent ---** Study staff will review both the documentation of the consenting process as well as a percentage of the completed consent documents. This review will evaluate compliance with the research protocol (and data collection training), accuracy, and completeness of data. Feedback will be provided to data collectors to ensure proper consenting procedures are followed.

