### 10.1.9 DATA HANDLING AND RECORD KEEPING

#### 1. 10.1.9.1 DATA COLLECTION AND MANAGEMENT RESPONSIBILITIES

Data collection will be the responsibility of the clinical trial data collection staff under the supervision of Principal Investigator, Methodologist, and Co-Investigators. While all will be responsible for accuracy, completeness, and timeliness of the data reported, the PI and Methodologist are taking lead on tracking and cleaning of all data in real time, and will give feedback as needed to data collectors to ensure accuracy, completeness, and timeliness. All source documents will be completed in a neat, legible manner to ensure accurate interpretation of data.

Data collectors will regularly and routinely log meta-data on the data collection in a share file that is de-identified. This enables them to communicate with one another which participants have had data collection for which measurement occasions.

Clinical meta-data (i.e. treatment dose date, time, duration, etc.) as well as outcome data (i.e. audio files of treatment dosages and transcripts) will be automatically collected via the Friendlybuzz system. Friendlybuzz and Qualtrics (two data storage systems) both include password protection and internal quality checks.

2.

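### The methodologist's blinding status is contradictory and undefined, and under the roles described the analyst cannot be blind to treated versus control.

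*Combined protocol and SAP*

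**What the plan says.** Section 6.3, on measures to minimise bias, limits the methodologist's access: "The methodologist will only have access to the participants' codes and raw data". It then gives the purpose: "They will remain blind to ensure the most objective analysis of the data". The same section says that the data team is separate from the treatment team and has no access to Friendlybuzz, the system that records the calls. It describes the other side of the line as follows: "The PI and graduate student(s) will have access to the unblinded data (i.e. both the older adults' names, codes, and baseline data" (the bracket closes after these words). The PI is also said to supervise scoring and random assignment.

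Section 9.4.6, on interim analyses, says that "the longitudinal multilevel modeling (growth modeling) analysis will be run after each cohort is completed", and then: "The methodologist running the analysis will remain unblinded throughout the analysis process". It adds that the final analysis will reuse the same code on the participants of all four cohorts.

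Section 10.1.8 says that the PI and the methodologist "will perform internal quality management of survey data (baseline and 5 measurement occasions) as well as the audio file and transcript data". Section 10.1.9.1 says that these two roles "are taking lead on tracking and cleaning of all data in real time", and that audio and transcripts are collected through Friendlybuzz.

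**The concern.** One role is described as blind where the plan lists its protections against bias, and as unblinded where the plan describes the analysis. A reader cannot tell which applies, or whether blinding refers to participants' identities, to their allocation, or to both.

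This matters because the same person co-leads cleaning and runs the growth model after each cohort, partly to see whether results are moving as hoped. Several choices remain open during that time. Section 9.1 lists many outcomes under the primary endpoint without naming one as primary. Section 9.4.2 describes both a baseline-adjusted post-intervention analysis and a longitudinal one. Section 9.4.1 leaves corrective procedures to be applied as recommended. If decisions on cleaning or modelling are made with allocation in view, a trial report that cites 6.3 would claim a protection that did not operate.

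**Working it through.** The plan gives no figure on this point, so the check sets its statements side by side.

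1. **Status.** 6.3: blind. 9.4.6: unblinded for the whole analysis. The role and the activity are the same. The two statements can agree only if the word means different things in the two places, and neither place defines it.

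2. **Firewall.** 6.3 bars the data team from Friendlybuzz. 10.1.9.1 says that audio and transcripts come from Friendlybuzz, and 10.1.8 has the methodologist share in their quality management. Exported files could be checked without a login, and 6.3 does not say whether the methodologist belongs to the data team. The passages therefore strain against each other; whether the firewall is breached depends on details that the plan does not give.

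3. **Does audio reveal treated versus control?** Planned arm sizes are 180 each (Section 9.2). Each treated participant is due 8 calls (6.1.2, 6.4), and controls receive none in the trial period (6.1.1).
   - Treated: 2 × 180 × 8 = 2,880 recordings at full delivery.
   - Control: 180 × 0 = 0 recordings.
   - Given at least one recorded call per treated participant, the existence of audio sorts all 3 × 180 = 540 participants. The optional calls for controls come two months later (6.4), and the system logs call dates, so they do not hide the split.

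4. **Does the model reveal it without audio?** Section 9.4.2 nests treated participants within callers and gives controls no caller level. The analysis file must therefore carry a caller identifier for treated participants only. Treated versus control is visible to whoever fits the model, under any label coding. That is also the comparison in the primary hypothesis (9.1).

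5. **BE versus BE WITH.** Neither the existence of audio nor the caller level separates these two arms. Call content or a list linking callers to their training would. Coded labels would mask this comparison if the analyst has neither source. No section describes coded labels, a second statistician, or a rule that separates the roles.

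6. **If 9.4.6 contains a slip and means blinded.** Steps 3 and 4 are unchanged. The contradiction in step 1 disappears, but the claim in 6.3 still cannot hold for treated versus control.

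**The case against.** The strongest reply is that blind in 6.3 may mean blind to identity. The section explains its unblinded data as names, codes and baseline data, without mentioning allocation. Its example of accidental unblinding concerns first names, and its planned unblinding is a report to a case manager. On that reading 6.3 and 9.4.6 could both be true. This has force, and it is why the status is called undefined as well as contradictory. It does not remove the problem. The heading of 6.3 and its appeal to objective analysis invite the allocation reading, and if identity was meant, no allocation-blind analysis was planned at all.

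The reuse of one code across cohorts is a partial safeguard and deserves credit. It has no lock date before the first look by arm, and it covers neither cleaning decisions nor the choice of which outcome to emphasise.

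Four stronger inferences are tempting but are not supported:
- *That no blinded analysis of any kind is possible, or that the results will be biased.* BE versus BE WITH can still be masked, and the roles described show opportunity for bias, not its occurrence.
- *That an inflated type I error can be attached to the unblinding.* Inflation from choosing among several analyses or outcomes arises equally for an analyst with masked labels, so such a figure would measure multiplicity.
- *That 9.4.6 should simply be changed to say blind.* By step 4 that would add a second inaccurate statement.
- *That cohort checks must be pooled over arms.* That would redesign the interim looks, whose stated purpose is to see trends. Resolving the blinding status does not require it.

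**Conclusion.** The point holds as an internal inconsistency with a practical consequence. The methodologist's blinding status is stated in opposite terms and defined nowhere. Blinding to treated versus control cannot hold under the roles and model described. Blinding to BE versus BE WITH could hold but is not arranged.

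The split is visible for all 540 planned participants and concerns the primary comparison. The resulting effect on estimates or error rates cannot be sized from the documents, and no figure is offered. The conclusion rests on two readings: that the methodologist in 6.3, 9.4.6, 10.1.8 and 10.1.9.1 is the same role, and that joint quality management of audio means that the methodologist handles at least some of it. Without the second reading, the caller level in the model still gives the same result. The correction should be made, and it is cheap.

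**What to change.** - Reconcile 6.3, 9.4.6, 10.1.8 and 10.1.9.1: state one blinding status for the methodologist and what it covers (identity, BE versus BE WITH, or both).
- State plainly that treated versus control cannot be masked from the analyst, because controls have no caller.
- Give the methodologist coded labels for BE and BE WITH, with caller identifiers that cannot be matched to the training list.
- Assign audio and transcript quality checks to the PI, who is already unblinded. The PI also co-leads cleaning, so this move alone does not protect cleaning decisions.
- For that reason, date-lock the outcome list, the data-cleaning rules and the model code before the first cohort is analysed. This is the only step that protects the primary comparison, which masking cannot reach. It also makes the same-code statement in 9.4.6 verifiable.

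The cost is protocol wording, a small role swap that puts more checking on the PI, and programming done earlier than planned. The cohort analyses can go ahead.

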### 8.3.5 ADVERSE EVENT REPORTING

There are no responsibilities of investigators for reporting of AEs outside of the study team and the clinical database with the exception of sustained suicide risk, which as previously noted will be reported to the case managers assigned to those particular older adult participants. This is noted in our MOUs with the 22 participating counties.

6.

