### 8.3.6 SERIOUS ADVERSE EVENT REPORTING

In consultation with the PI, a trained member of the study team will be responsible for conducting an evaluation of a serious adverse event and shall report the results with the sponsor, and if relevant the participating AAAs (Area Agencies on Aging).

7.

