### 8.4.2 UNANTICIPATED PROBLEMS REPORTING

The Principal Investigator will report any unanticipated problems (UPs) to the Institutional Review Board (IRB) and to the sponsor.

Any UP report will include the following information:

- Grant #/IRB #
- A detailed description of the event, incident, experience, or outcome
- An explanation of the basis for determining that the event, incident, experience, or outcome represents an UP
- A description of any changes to the protocol or other corrective actions that have been taken or are proposed in response to the UP

To satisfy the requirement for prompt reporting, UPs will be reported using the following timeline:

- UPs that are serious adverse events (SAEs) will be reported to the PI's Office of Research and Compliance (IRB) within 7 days of when they arise
- If there are any deviations from the protocol, a protocol deviation form will be submitted to the Office of Research and Compliance within 7 days of the deviation
- Upon reconciliation of the deviation, the PI will provide written documentation through federal monitoring reports of any AEs and/or protocol deviations

3. PARTICIPANTS	8.4.3 REPORTING	UNANTICIPATED PROBLEMS	TO
N/A			

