#### 10.1.2 STUDY DISCONTINUATION AND CLOSURE

This study may be temporarily suspended or prematurely terminated if there is sufficient reasonable cause. Written notification, documenting the reason for study suspension or termination, will be provided by the suspending or terminating party to study participants, investigator, funding agency, and regulatory authorities. If the study is prematurely terminated or suspended, the Principal Investigator (PI) will promptly inform study participants, the Institutional Review Board (IRB), and sponsor/funding agency and will provide the reason(s) for the termination or suspension. Study participants will be contacted, as applicable, and be informed of changes to study schedule.

Circumstances that may warrant termination or suspension include, but are not limited to:

- Determination of unexpected, significant, or unacceptable risk to participants
- Insufficient compliance of study staff to the protocol
- Determination that the primary endpoint has been met
- Determination of futility
- The funding that has been secured is cut early and abruptly

The study may resume once concerns about safety, protocol compliance, and data quality are addressed, and satisfy the funding agency, sponsor, IRB, or other relevant regulatory or oversight bodies.

---

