**Source documents and the electronic data ---** Data will be initially captured on source documents (see **Section 10.1.9, Data Handling and Record Keeping**). To ensure accuracy, study staff will compare a representative sample of source data against the database, targeting key data points in that review.

**Intervention Fidelity** — Consistent delivery of the study interventions will be monitored throughout the intervention phase of the study. Procedures for ensuring fidelity of intervention delivery are described in **Section 6.2.1, Interventionist Training and Tracking**.

**Protocol Deviations** – The study team will review protocol deviations on an ongoing basis and will implement corrective actions when the quantity or nature of deviations are deemed to be at a level of concern.

Should independent monitoring become necessary, the PI will provide direct access to de-identified source data/documents, and reports for the purpose of monitoring and auditing by the sponsor/funding agency, and/or inspection by local and regulatory authorities.

9.

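### Section 9.4.6 says without qualification that no safety finding would pause treatment, which conflicts with 10.1.2; secondarily, no section says the named monitor or evaluator sees event data

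*Combined protocol and SAP*

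**What the plan says.** **Suspension.** Section 9.4.6 runs the growth model after each of four cohorts, partly to learn "if there are any issues that need to be addressed", and says the endpoints are monitored daily. It then states: "There are no temporary suspension or safety findings that would prompt temporary suspension of the treatment". Section 10.1.2 says the study may be suspended or ended early for reasonable cause. Its first listed circumstance is "Determination of unexpected, significant, or unacceptable risk to participants". Written notice "will be provided by the suspending or terminating party", but the section does not say who that party is or who determines that the risk is unacceptable.

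**Event data.** Adverse events go into a lab tracking file (8.3.4) and are assessed by the principal investigator and suitably trained clinicians or researchers (8.3.3). Section 8.3.5 says investigators have no responsibility for "reporting of AEs outside of the study team and the clinical database with the exception of sustained suicide risk". For serious events, a study team member evaluates and "shall report the results with the sponsor, and if relevant the participating AAAs" (8.3.6). Unanticipated problems go to the IRB and sponsor. Section 8.4.2 adds that, once a deviation is reconciled, "the PI will provide written documentation through federal monitoring reports of any AEs and/or protocol deviations". Section 10.1.8 adds: "Should independent monitoring become necessary, the PI will provide direct access to de-identified source data/documents"; that access is for the sponsor, funder and authorities.

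**Oversight.** Section 10.1.5 lists a medical or independent safety monitor without duties. Section 10.1.6 gives safety oversight to an independent external evaluator, who makes checks while the trial runs. Neither section mentions adverse event data. Section 9.4.4 (Safety Analyses) is marked not applicable.

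**The concern.** The two sections give different instructions for the same situation. If a cohort analysis or the daily monitoring showed participants in a called arm getting worse, 9.4.6 as written says treatment continues, while 10.1.2 says it may be paused. A coordinator or methodologist working from the statistical section would find the first instruction and no pointer to the second.

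This matters more here than in many trials of a phone intervention. Participants are screened on loneliness, thwarted belongingness and social provisions, and suicidality is a target of the treatment. The sections disagree on whether low-risk people are enrolled: 8.1 excludes them, while sections 3, 4.1 and 9.4.7 plan for them. On either reading, medium- and high-risk people are included.

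The second point follows from the first. With no safety analysis planned, a pattern across arms would have to be noticed by someone reading the events. The plan names independent people who could do this but does not say that they see the events.

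**Working it through.** The plan states no figure on this point, so there is nothing to reproduce. The check is a comparison of text, with two counts.

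1. **Do 9.4.6 and 10.1.2 concern the same act?** The first speaks of suspending the treatment, the second of suspending the study. Suspending the study would ordinarily halt the calls, and the calls are the treatment. The difference in noun does not reconcile the sections.

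2. **Is the 9.4.6 sentence limited to formal stopping rules?** Its place under Planned Interim Analyses suggests that intent. Its wording covers safety findings generally, and the same paragraph describes daily monitoring and looking for problems. Nothing in it narrows the scope or points to 10.1.2.

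3. **How many looks does it cover?** There are four cohorts, and the last one yields the final analysis: 4 − 1 = 3 looks before the final, plus the daily monitoring.

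4. **Who decides under 10.1.2?** No role is named for the risk determination.

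5. **Where do event data go?**

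| Route | Section | Recipient | Names monitor or evaluator? |
|---|---|---|---|
| Adverse events | 8.3.5 | Study team and database; sustained suicide risk to case managers | No |
| Serious adverse events | 8.3.6 | Sponsor; Area Agencies on Aging if relevant | No |
| Unanticipated problems | 8.4.2 | IRB and sponsor | No |
| Federal monitoring reports | 8.4.2 | Federal funder | No |
| Source data, if independent monitoring becomes necessary | 10.1.8 | Sponsor, funder, authorities | No |

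6. **Would the log show a difference between arms?** The fields listed in 8.3.4 do not include treatment condition. Section 6.3 keeps condition in a separate file indexed by participant code, so the two can be linked, but only as a deliberate step.

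7. **Are raw counts comparable across arms?** Under 8.3.4, data collectors and treatment providers each record events that come up in their own contacts. After baseline, 6.4 gives the called arms 8 calls + 4 measurement occasions = 12 contacts, and control 4. That is 12 / 4 = 3 times as many occasions to record an event, so higher raw counts in the called arms could arise from contact alone.

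**The case against.** The strongest reply is that this is a missing cross-reference. In context, the 9.4.6 sentence most naturally says that the interim analyses carry no stopping rule, and 10.1.2 leaves the power to suspend intact. There is also real safety machinery. Investigators and clinicians grade severity, relatedness and expectedness (8.3.3). Unanticipated problems go to the IRB and sponsor with any corrective action, and those that are serious events go to the IRB within 7 days (8.4.2). Participants at risk receive crisis resources and referral to a case manager (8.2). Resuming a suspended study must satisfy the funder, sponsor, IRB or other oversight bodies (10.1.2). Section 2.3.3 rates the risk of taking part as very low.

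Most of this stands, and it limits the point. A reader might infer that the protocol forbids suspension; 10.1.2 shows that it does not. A reader might infer that independent oversight or event reporting is absent; 10.1.6 and the routes above show otherwise, and the evaluator's checks may already cover events in practice. Nor is keeping condition out of the event log a defect: 6.3 separates the files to guard against bias.

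What the reply does not remove is the sentence itself. It states a rule on participant safety, and that rule disagrees with another section. The individual safeguards act on one person at a time and would not by themselves reveal one arm doing worse.

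**Conclusion.** The conflict between 9.4.6 and 10.1.2 holds on the text and should be corrected. The sentence applies at three looks before the final analysis and throughout daily monitoring. The point about the monitor and evaluator holds in a narrower form: what is missing is a statement of which event data that person sees and when. It rests on the public text available, from which some pages are omitted.

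The final estimate, error rate and power do not change. The number of participants affected cannot be estimated, because no event rate is given. It is tempting to size the concern by how much harm an early cohort analysis could detect, but that would not measure it. Precision on the outcome scales says nothing about who may pause treatment or who reads the event log, and the documents give no cohort sizes and do not say whether the looks are cumulative.

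**What to change.** - **9.4.6:** replace the sentence with: 'No statistical stopping rule is pre-specified. Any safety concern seen at a cohort analysis or in daily monitoring is referred for a suspension decision under 10.1.2.'
- **10.1.2:** name who makes that decision. The grounds for pausing are for the sponsor, IRB and monitor to set.
- **10.1.6, with a matching exception in 8.3.5:** state that the monitoring checks include review of the de-identified adverse event and serious adverse event log at each cohort look, linked by participant code to treatment condition, by the monitor or evaluator already named.
- **Two cautions to write in.** The reviewer should be treated as unmasked: control has no treatment providers, so an event that came up on a call identifies a called arm even if the arms are coded. Raw counts should be read with the 12-versus-4 difference in contacts in mind. Restricting the comparison to events recorded by data collectors is not a safe cure, because it could miss events disclosed only on calls.
- **Leave unchanged** the sponsor, IRB, federal-report, Area Agency and case-manager routes.

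The cost is wording in four sections, a small linking step at each look using files the lab already holds, and a short review by a person already named, three times before the final analysis. It needs no new participant data, staff or sample size.
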